4 PATIENT SELECTION

4.1 Eligibility criteria

The patient must fulfil the eligibility criteria (listed in Sections 4.1.1 and 4.1.2).

4.1.1 Inclusion criteria:

- 1. Part 1:
 - Histologically or cytologically proven advanced solid tumour or Lymphoma, refractory to conventional treatment or for which no conventional therapy exists (if the diagnosis is confirmed by cytology and no follow-up historical tumour sample has been obtained, the patient will not be eligible).
 - Available archived tumour samples.

Part 2:

- Histologically proven DLBCL or BL, which is relapsed or refractory or both to conventional treatment or for which no conventional therapy exists or has been refused by the patient. (Refractory disease is defined as either progressive disease as the best response to the last line of systemic therapy or stable disease as the best response after at least two cycles of the last line of therapy with stable disease duration lasting no longer than six months from the last dose of the last line of systemic therapy. Relapsed disease is defined as disease that responded partially or completely to the last line of therapy and has since progressed).
- Confirmed available tumour samples which can be obtained and used for the study to confirm MCT1 and MCT 4 expression (it is acceptable for the result to be reported after the patient has started study treatment) as demonstrated by IHC.
- Measurable disease according to RECIST criteria version 1.1 or International Working Group criteria for Lymphoma
- 2. Life expectancy of at least 12 weeks
- 3. World Health Organisation (WHO) performance status of 0 or 1 (Appendix 1)
- 4. Haematological and biochemical indices within the ranges shown below.

Laboratory Test	Value required (For both Parts 1 and 2 except where specified)
Haemoglobin (Hb)	\geq 9.0 g/dL (90 g/L) or \geq 10.0 g/dL (100 g/L) if transfusion within last 4 weeks
Absolute neutrophil count (ANC)	Part 1: ≥ 1.5 x 10 ⁹ /L Part 2: ≥ 1.0 x 10 ⁹ /L
Platelet count	Part 1: ≥ 100 x 10 ⁹ /L Part 2: ≥ 50 x 10 ⁹ /L
Serum bilirubin	\leq 1.5 x upper limit of normal (ULN)
Alanine amino-transferase (ALT), aspartate amino-transferase (AST) and alkaline phosphatase (ALP)	\leq 2.5 x ULN or \leq 5 x ULN in presence of liver metastases (ALP \leq 5 x ULN in presence of bone metastases)
GFR	

Either:	
Calculated creatinine clearance (using the Wright or Cockcroft-Gault formula)	≥ 50 mL/min
Or :	
Isotope clearance measurement	
(uncorrected)	
Prothrombin time (PT)	<1.5 x ULN
Glucose (fasting)	<7.8 mmol/L
Lactate	Between 0.5 and 2.5 mmol/L inclusive
Bicarbonate	Between 22 mmol/L and 1.5 x ULN inclusive

5. LVEF>50%

6. 18 years or over7. Written (signed and dated) informed consent and be capable of co-operating with treatment and follow-up

4.1.2 Exclusion criteria:

- Radiotherapy (except for palliative reasons), endocrine therapy, immunotherapy or chemotherapy during the previous four weeks (six weeks for nitrosoureas, Mitomycin-C and 4 weeks for investigational medicinal products) before treatment.⁵ Shorter wash out periods may be acceptable if patient has recovered from therapy related toxicity and is at least five terminal half-lives post last administration. This should be discussed and agreed with the CDD and CI.
- 2. Ongoing toxic manifestations of previous treatments greater than NCI CTCAE Grade 1 at the time of starting study treatment. Exceptions to this are alopecia or certain Grade 2 toxicities, which in the opinion of the Investigator and the CDD should not exclude the patient.
- 3. Symptomatic brain or leptomeningeal metastases.
- 4. Patients with known retinal disease or macular degeneration affecting visual acuity as assessed by ophthalmologic tests.
- 5. Female patients who are able to become pregnant (or are already pregnant or lactating). However, those patients who have a negative serum or urine pregnancy test before enrolment and agree to use two forms of contraception (one highly effective form plus a barrier method) [oral, injected or implanted hormonal contraception and condom; intra-uterine device and condom; diaphragm with spermicidal gel and condom] or agree to sexual abstinence, effective from the first administration of AZD3965, throughout the trial and for six months afterwards are considered eligible.⁶
- 6. Male patients with partners of child-bearing potential (unless they agree to take measures not to father children by using a barrier method of contraception [condom plus spermicide] or to sexual abstinence effective from the first administration of AZD3965, throughout the trial and for six months afterwards. Men with partners of child-bearing potential must also be willing to ensure that their partner uses an effective method of contraception for the same duration for example, hormonal contraception, intrauterine device, diaphragm with spermicidal gel or sexual abstinence). Men with pregnant or lactating partners must be advised to use barrier method contraception (for example, condom plus spermicidal gel) to prevent exposure of the foetus or neonate.⁶
- 7. Any major surgery in the preceding eight weeks prior to the start of treatment or major thoracic or abdominal surgery from which the patient has not yet recovered
- 8. Patients who are unable to swallow oral medication.
- Alterations to corticosteroid dose within 2 weeks prior to first dose of AZD3965. An exception to this is usage of prednisolone or an equivalent steroid which is acceptable during screening but must be stopped at least 72 hours days prior
- 10. Gastrointestinal disorders likely to interfere with absorption of the study drug (e.g. partial bowel obstruction or malabsorption).
- 11 At high medical risk because of non-malignant systemic disease including active uncontrolled infection.
- 12 Known to be serologically positive for hepatitis B, hepatitis C or human immunodeficiency virus (HIV). (N.B. Mandatory testing not required).
- 13 History of serious allergy or auto-immune disease.
- 14. Diabetes mellitus treated with oral anti-diabetic medication (patients with diet controlled or insulin controlled diabetes may be included with fasting glucose <7.8 mmol/l and normal HbA1c).
- 15. Cardiac conditions as follows:
 - Clinically significant cardiovascular event within 6 months prior to study entry to include:
 - a. Acute coronary syndrome (myocardial infarction or unstable angina)
 - b. congestive heart failure requiring therapy;

⁶ Abstinence is only considered to be an acceptable method of contraception when this is in line with the preferred and usual lifestyle of the subject. Periodic abstinence (e.g., calendar, ovulation, symptothermal, post-ovulation methods) and withdrawal are not acceptable methods of contraception

⁵ Baseline measurements must be performed within four weeks before the patient receives the first dose. The interval between the last anti-cancer therapy and these measurements must be at least four weeks (28 days). Shorter wash out periods may be acceptable if patient has recovered from therapy related toxicity and is at least five terminal half-lives post last administration. This should be discussed and agreed with the CDD and Cl.

- Severe valvular heart disease (as defined by British Society of Echocardiography see Appendices 6)
- Presence of an atrial or ventricular arrhythmia, other than atrial fibrillation with well controlled ventricular rate, for which treatment is indicated (anti-arrhythmic drugs or implantable cardioverter defibrillator)⁷
- Second degree Mobitz type 1 (Wenckebach) heart block with symptoms, or second degree Mobitz type 2 or third degree heart block with or without symptoms, are exclusions unless the patient has a functional pacing system⁷
- QTc > 450 msec in adult male and > 460 msec in adult females (QTc to be verified manually (QTcF correction))
- History of congenital long QT syndrome
- History of Torsade de Pointes (TdP) (or any concurrent medication with a known risk of QT prolongation) – See Appendix 3for further details
- Uncontrolled hypertension (BP \geq 160/100mmHg despite medical therapy)
- 16. Patients who have had extensive radiotherapy to greater than 25% of bone marrow within 8 weeks. Prior autologous bone marrow transplant will not exclude a patient
- 17 Is a participant, or plans to participate in another interventional clinical trial, whilst taking part in this Phase I study of AZD3965. Participation in an observational trial or interventional clinical trial which does not involve administration of an IMP would be acceptable.
- 18 Any other condition which in the Investigator's opinion would not make the patient a good candidate for the clinical trial.
- 19. For Part 2 only: Current malignancies of other types, with the exception of adequately treated cone-biopsied *in situ* carcinoma of the cervix uteri; basal or squamous cell carcinoma of the skin; and patients with low risk prostate cancer on surveillance (with a Gleason score of ≤6 and a PSA of ≤10)

4.2 Patient enrolment

Before enrolling the patient in the trial, the Investigator or designated representative should determine the eligibility of the patient during the trial screening period. This determination must be clearly documented in the patients' hospital records.

Eligible patients must be enrolled in the electronic data capture (EDC) system by site staff and then registered at the CDD before they start treatment with AZD3965. If the patient is eligible for the trial, then a patient number will be automatically allocated by the EDC system during the enrolment process. The CDD will send confirmation of the patient registration including the assigned dose level to the Investigator following enrolment of the patient. Study treatment may only be administered after confirmation has been received.

5 TREATMENT

5.1 Selection of the Phase I starting dose and schedule (Part 1)

The starting dose was 5 mg given as a capsule once daily.

The justification for the starting dose can be found in Section 2.2.7

5.2 Maximum Exposure Limit

CRUKD/12/004 AZD3965 Protocol Version 14.0_FINAL_04Feb2020 EudraCT number: 2010-024463-41

5.3 Dosing schedule/treatment schedule (Parts 1 and 2)

For Part 1 of the study, AZD3965 was administered orally on Day -7 and then continuously for a 28 day cycle starting on Day 1.

For Part 2 of the study, AZD3965 will be administered orally continuously for a 28 day cycle starting on Cycle 1 Day 1. There will be no administration of AZD3965 on Day -7 in Part 2 of the study.

In Part 1, the total daily dose was initially administered once daily and was reviewed throughout Part 1, the total daily dose was spilt into a twice daily dosing schedule.

In both Part 1 and 2 a maximum of six cycles will be administered (further cycles can be given upon review of the data and approval by CRUK CDD where patients are benefiting from receiving AZD3965 i.e. tumour assessments show a stable or partial/complete response, refer to Section 5.7).

The AZD3965 capsules must be swallowed whole (with water) and not chewed, crushed, dissolved or divided.

Patients in Part 1 were instructed to take AZD3965 with food, except for their first dose at Day -7 which was taken fasted. In Part 2 as there is no Day -7 dose, AZD3965 is to be taken with food and should be taken at the same time(s) every day.

For the once daily dosing in Part 1, the total daily dose of AZD3965 was taken at the same time once a day, and for twice daily dosing, the total daily dose of AZD3965 was spilt into two doses and should be taken in the morning and 12 hours later, respectively.

In Part 2 a twice daily dosing is planned unless emerging data suggests a once daily dosing is indicated.

On the days of PK sampling (see Section 9.4.1) patients should take their scheduled dose at the hospital so that the exact time of administration can be recorded.

In cases of toxicity, treatment may be interrupted and then resumed when all toxicities have returned to Grade 1 or lower. In the event of Grade 3 or 4 QTc prolongation (QTc interval >500 msecs or increase of > 60 msecs from baseline (QTcF correction)), treatment with AZD3965 will be withdrawn.

Intermittent dosing schedules and administration with or without food may be explored based on observed toxicities or if continuous daily dosing is not tolerated at levels that inhibit MCT1.

5.4 Dose escalation scheme (Part 1)

Each patient cohort included a maximum of six evaluable patients following a rolling six dose escalation scheme (Skolnik A.M. *et al.*, 2008).

The starting dose was 5 mg given as an oral capsule. 5, 10, 20, and 30 mg capsules can be manufactured. Pharmacokinetic assessments were performed during this cohort to assess the potential half-life of AZD3965 in order to inform whether dosing for future cohorts should be once or twice daily. The next total daily dose level will be 10 mg either once daily or split into two daily doses.

The total daily dose was doubled in successive cohorts until an NCI CTCAE Version 4.02 Grade 2 highly probably or probably related adverse drug reaction was reported. Subsequent dose increases between cohorts was up to a maximum of 50% driven by reported safety, PK and PD data. If continuous daily dosing is not tolerated at levels that inhibit MCT1 then intermittent schedules will be explored.

A maximum of six evaluable patients were treated at each dose level with at least one male patient in each cohort. It is acceptable that the fourth, fifth and sixth patients can begin treatment at the same time as the second and third patients which must be after the first patient has completed Cycle 1 Day 7 of treatment although this will be assessed and confirmed by the CDD based on emerging data from the study.

The dose level of AZD3965 was assigned according to the number of patients already enrolled at the current dose level, the number of DLTs (and any other drug-related AEs) observed at the current dose level and the number of patients enrolled who are at risk of developing a DLT (see Section 3.2 Definition of dose limiting toxicity). When sufficient data, as deemed by the Sponsor and CI, was available to assess these, the AZD3965 dose level was assigned according to the following:

- If the data is available from a minimum of three patients who have been treated in a cohort and no DLTs have been observed at that dose level, then dose escalation can be considered.
- If the data is available from three patients who have been treated in a cohort and one DLT has been observed at that dose level, then the cohort will be expanded to include at least 6 patients.
- If two DLTs have been observed at any dose level, the dose will be de-escalated and the
 previous total daily dose level will be expanded to include up to six patients. If the previous total
 daily dose level already included a cohort of six patients then this will be identified as the MTD.
 If a patient has already started treatment at a higher dose level at the time when two DLTs are
 identified at a lower dose level, their dose will be assessed and confirmed by the Sponsor based
 on the reported safety data.
- If not all data are available from at least three patients in order to take a decision on dose escalation but an eligible patient is ready to begin treatment, the dose level will remain the same. Up to six patients may be enrolled at that dose level.

Twenty-eight days of data (safety and PK) should be available for a minimum of three evaluable patients in a cohort in order to make the decision to dose escalate.

The decision to continue with dose escalations was guided by drug exposure. Assessments of drug exposure was based on Day -7, Day 1 and Day 29 PK from Part 1 only. Drug exposure was not to exceed the maximum exposure limit as set out in Section 5.2. If PK data from any of these time points indicated that the exposure cap has been exceeded, the cohort would be completed (toxicity permitting) but no further dose-escalations will take place.

5.4.1 Intra-patient dose escalations

No intra-patient dose escalation is allowed.

5.4.2 Expansion of dose level(s)

If one instance of DLT (as defined in Section 3.1.3) was observed in three patients, at least six evaluable patients would be treated at that dose level. If one out of six patients experienced a DLT, dose escalation would continue. If two out of up to six (i.e. between two and six) patients experience a DLT dose escalation would stop and this dose would be defined as the maximum administered dose (MAD). At least six patients would be treated at the total daily dose level below the MAD to define the MTD.

The MAD could also equal the MTD in the event that dose escalation was stopped before two DLTs were observed at a given dose level, due to the expectation that higher dose levels would be too toxic to administer to patients.

5.5 Dose modifications

5.5.1 Dose withdrawal

In the event of CTCAE Grade 3 or 4 QTc prolongation (QTc interval >500 msecs or increase of >60 msecs from baseline (QTcF correction)) treatment with AZD3965 will be withdrawn.

5.5.2 Dose reductions

In Part 1 the dose of AZD3965 would be reduced to the previous dose level for any patient who experienced a DLT (with the exception of QTc prolongation, these patients would be withdrawn from the trial, see Section 5.5.1). If a patient had a dose reduction, their dose would not be re-escalated.

Treatment at the reduced dose would start when the toxicities had resolved to Grade ≤1 or returned to baseline (if within 14 days).

If the patient experienced the same or different DLT toxicity again at this reduced dose, there would be no further dose reductions and the patient was withdrawn from the study.

In Part 2, the PK profile of AZD3965 and patient safety data will be reviewed after the first three evaluable patients. Following this review, the RP2D may switch to once or twice daily dosing (at the same total daily dose level) or a lower total daily dose at the discretion of the CDD and CI. Any DLTs experienced during Part 2 will be collected to assist with assessment of patient safety profiles and the RP2D may be adjusted accordingly.

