In both Parts 1 and 2, AZD3965 will be administered as continuous daily dosing in 28 day cycles for up to six cycles. If the patient is benefitting from the treatment, a further six cycles may be administered after discussions between the Investigator and the Sponsor, Cancer Research UK's Centre for Drug Development (CRUK CDD). In the case of toxicity, treatment will be interrupted and then resumed when all toxicities have returned to Grade 1 or baseline. Intermittent dosing schedules may be explored based on observed toxicities.

In Part 2 all patients will be treated at the RP2D determined in Part 1. There will be no Day -7 dose in Part 2. All patients in Part 2 will be treated at the RP2D as continuous daily dosing in 28 day cycles for up to six cycles starting on Day 1. If the patient has not progressed after six cycles, further cycles may be given after discussion between the Investigator and the CDD (see Section 5.7).

An interval of 14 days (from Cycle 1 Day 1) must be observed between the recruitment of the first and second patient in the expansion cohort but subsequent patients can be treated in parallel. Data must be available (safety and PK) for a minimum of three evaluable patients in order to make any decision to change the Part 2 dose (RP2D). Any changes to the Part 2 dose (RP2D) will be for safety reasons and to decrease the total daily dose only.

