1	5 mg once daily (OD)
2	10 mg OD
3	20 mg OD
4	30 mg OD
5	15 mg twice daily (BD)
6	10 mg BD

Part 2

In Part 2, up to 20 evaluable patients with DLBCL or BL will be treated at the RP2D from Part 1 of the study. There will be no administration of AZD3965 on Day -7 in Part 2 of the study. AZD3965 will be administered as continuous daily dosing in 28 day cycles starting from Cycle 1 Day 1 for up to six cycles. If the patient has not progressed after six cycles, further cycles may be given after discussion between the Investigator and the CDD and written approval given by the CDD, refer to Section 5.7. In the case of toxicity, treatment will be interrupted and then resumed when all toxicities have returned to Grade 1 or lower. Intermittent dosing schedules may be explored based on observed toxicities.

An interval of 14 days (from Cycle 1 Day 1) must be observed between the recruitment of the first and second patient in the expansion cohort but subsequent patients can be treated in parallel. Data must be available (safety and PK) for a minimum of three evaluable patients in order to make any decision to change the Part 2 dose (RP2D). Any changes to the Part 2 dose (RP2D) will be for safety reasons and to decrease the total daily dose only.

The study was designed in accordance with the EMEA Guideline on strategies to identify and mitigate risks for first-in-human clinical trials with investigational medicinal products.

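### Section 5.5.2 fixes what happens to a patient after a DLT in Part 1 only; for a recovered Part 2 DLT that is neither a QTc nor an ERG event, no restart dose and no second-DLT action is set

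*Protocol*

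**What the plan says.** Section 5.5.2 sets a patient-level rule for Part 1: "In Part 1 the dose of AZD3965 would be reduced to the previous dose level for any patient who experienced a DLT". QTc events are excepted because those patients are withdrawn. It continues: "If a patient had a dose reduction, their dose would not be re-escalated". Treatment at the reduced dose starts once toxicity is back to Grade 1 or less, or to baseline, within 14 days. If a DLT recurs at the reduced dose, "there would be no further dose reductions and the patient was withdrawn from the study".

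Part 2 then gets its own paragraph in 5.5.2. It provides for a PK and safety review after three evaluable patients, a possible change of schedule or a lower total daily dose, and this: "Any DLTs experienced during Part 2 will be collected to assist with assessment of patient safety profiles and the RP2D may be adjusted accordingly".

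Elsewhere, section 1.4 says "In Part 2 all patients will be treated at the RP2D determined in Part 1". On toxicity, section 1.4 has "In the case of toxicity, treatment will be interrupted and then resumed when all toxicities have returned to Grade 1 or baseline", and section 3.3, under Part 2, has "In the case of toxicity, treatment will be interrupted and then resumed when all toxicities have returned to Grade 1 or lower". Section 3.3 adds: "Intermittent dosing schedules may be explored based on observed toxicities". None of these sentences names a restart dose.

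**The concern.** The rule in 5.5.2 refers to a reduced dose that only its Part 1 sentence creates, so it does not carry over to Part 2. The Part 2 text works at the level of the cohort dose. A Part 2 patient whose DLT has recovered is therefore covered by a statement that treatment resumes, with no step-down and no consequence attached to a second DLT.

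Part 2 is meant to explore further how tolerable the RP2D is. The same recovered event that required a lower dose in Part 1 is left to case-by-case judgement here, and sites in a multi-centre trial have no common written rule to follow.

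**Working it through.** The plan states no figure on this point, so the check is mainly textual.

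**Step 1. Remove the Part 2 DLTs that already have a fixed patient-level action.**
- QTc DLT: treatment withdrawn (5.3, 5.5.1).
- All three Part 2 ERG criteria: withdrawal, either at once or if not resolved within two weeks (3.1.4, Appendix 4).
- Any toxicity not recovered after a two-week delay: withdrawal (5.5.3).

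**Step 2. What remains.** From 3.1.4: haematological DLTs, cardiac DLTs other than QTc, and other Grade 3 or 4 toxicity including biochemical events, where these recover within two weeks. Haematological events are not remote: Part 2 admits patients with ANC from 1.0 and platelets from 50 (x 10⁹/L), against 1.5 and 100 in Part 1 (4.1.1).

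**Step 3. Which texts could supply the missing rule?**

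| Text | What it does | Restart dose fixed? | Second-DLT action fixed? |
|---|---|---|---|
| 5.5.2, Part 1 paragraphs | One level down, then withdrawal | Part 1 only | Part 1 only |
| 5.5.2, Part 2 paragraph | Review and adjustment of the RP2D | No | No |
| 1.4, 3.3 | Change of the Part 2 dose, downward only, on data from at least three evaluable patients | No | No |
| 3.1.4 | Dose may be adjusted in the light of Part 2 DLTs | No | No |
| 3.3, 5.3, 5.5.3 | Intermittent schedules may be explored | No | No |
| 5.7, 12 | Stop for unacceptable toxicity, or withdraw for an AE or SAE, by judgement | No | No |
| 10.6, 15.1 | Urgent safety measures; sponsor-approved deviations | No | No |

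The RP2D-level change needs three evaluable patients, so it cannot serve a DLT in the first or second patient. The toxicity condition in 5.7 (no Grade 2 or greater drug-related event, with sponsor review) applies to requests to go beyond six cycles, not to restarts within Cycles 1 to 6.

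**Step 4. Could Part 1 make Part 2 DLTs negligible?** Section 1.2.1 accepts a dose with at most one DLT in up to six patients. If six were treated, the exact (Clopper-Pearson) 95% intervals for the true rate are:
- 0 of 6: upper limit 1 − 0.025^(1/6) = 0.459, so 0 to 46%.
- 1 of 6: 0.004 to 0.641, so 0.4 to 64%.

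For illustration, take an assumed DLT rate p in 20 Part 2 patients. The expected number is 20p, and P(at least one) = 1 − (1 − p)^20.

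| Assumed p | Expected DLTs | P(at least one) |
|---|---|---|
| 5% | 1.0 | 0.64 |
| 10% | 2.0 | 0.88 |
| 1/6 | 3.3 | 0.97 |
| 25% | 5.0 | >0.99 |

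These counts include QTc, ERG and unrecovered DLTs, so at each assumed rate they are upper bounds for the group at issue.

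**Step 5. Size of the step that Part 2 lacks.** The cohorts in 3.3 had total daily doses of 5, 10, 20, 30, 30 (15 mg BD) and 20 (10 mg BD) mg. The next lower total daily dose is 30 to 20 mg (20/30 − 1 = −33%) or 20 to 10 mg (10/20 − 1 = −50%).

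**The case against.** A reader might infer that the protocol expressly sends a Part 2 patient back to the causative dose. The documents do not support that. The section 1.4 sentence on resuming treatment stands in a paragraph covering both parts, and in Part 1 it coexisted with a mandatory reduction. It says when to restart, not at what dose. Treating all Part 2 patients at the RP2D can be read as assigning the cohort dose, and 3.1.4 can be read as allowing individual adjustment. Restart at the causative dose is therefore permitted, not prescribed.

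A reader might also take the previous dose level in 5.5.2 to mean the previous cohort number, which would not always lower the dose. That is strained: 3.1.5, 5.4 and 5.4.2 step by total daily dose level, and 5.4.1 forbids escalation within a patient.

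The stronger defence is context. Part 1 climbed through untested doses, whereas Part 2 uses one dose chosen on safety and PK. Part 2 has a 14-day gap after the first patient and downward-only changes. DLTs are reported to the sponsor within 24 hours (10.2.2), and safety data are reviewed regularly (10.5). A mandatory cut would also catch a recovered Grade 3 biochemical event, and case-by-case judgement is a defensible choice in relapsed or refractory lymphoma.

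These points lower the risk and make divergent handling less likely. They do not supply a restart dose or a second-DLT action, and the protocol does not say that case-by-case handling was the intended policy.

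**Conclusion.** The gap is real within its limits. For Part 2 DLTs that recover within two weeks and are neither QTc nor ERG events, the protocol mandates no dose reduction and no stop after a second such DLT. Following the text can therefore give a patient less protection than the trial's own Part 1 rule.

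How many patients this touches cannot be estimated, since the readable text gives neither the RP2D nor its DLT rate. The figures above rest on assumed rates and on six patients treated at the selected dose. The conclusion also rests on reading the Part 1 reduction rule as confined to Part 1, which the wording and layout of 5.5.2 support.

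This should be corrected by amendment. Sponsor oversight and the discretionary routes keep it from being more serious. A patient-level dosing rule belongs in the protocol, so it is not a matter to leave to the SAP.

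**What to change.** Add a Part 2 paragraph to 5.5.2 and cross-refer to it from 1.4 and 3.3:
- After a first DLT that has resolved to Grade 1 or less, or to baseline, within 14 days, any restart is at the next lower total daily dose explored in Part 1 (30 to 20 mg, or 20 to 10 mg).
- The sponsor states that dose and its schedule in mg. Of the listed cohorts, 10 mg total daily was studied only as 10 mg once daily; 5 mg twice daily was not a cohort.
- No re-escalation, and withdrawal on any further DLT.
- The QTc, ERG and two-week withdrawal rules stand unchanged.

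Flag patients on a reduced dose in the safety tables (14.2) and the response listings (14.5). Section 14.1 already requires dose modifications to be described, so this is a small addition.

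The cost is one paragraph, two cross-references and a flag, with no added patients, procedures or capsule strengths. The downside is that a few patients receive less than the RP2D, which slightly dilutes the single-dose safety and response data; the flag makes that visible.
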